5.3 Endpoints

There is one primary endpoint and one secondary endpoint in this clinical investigation.

5.3.1 Primary Endpoint

Concordance between LFP derived predictions and clinically optimized stimulation parameters

In this project we will establish the feasibility of recording LFP data intra-operatively from DBS electrode contacts using a multi-channel, high throughput data acquisition system and investigate if patterns in LFP can be used to select the optimal contacts for patient programming. Establishing the role of identifying and localizing LFP patterns intraoperatively can play an essential role in assisting the clinician who is programming the patient to select the optimal contact, especially when electrodes with multiple contacts (>8) are employed during DBS therapy. In this scenario, conventional techniques employing systematic contact evaluations in various combinations will be impractical due to time constraints.

The recently developed directional lead of SJM with 1-3-3-1 configuration offers the possibility of recording LFP activity from multiple directions. The primary utility of the segmented electrode is to steer the stimulation such that the side effects can be minimized. However, multiple contacts (n=8) on the electrode increase the programming complexity. In this project, we aim to determine in a blinded manner whether LFPs can guide programming. The outcomes of this pilot project will establish the scientific basis for whether LFPs recorded from a segmented electrode can be used for clinical decision making and to fine tune stimulation parameters.

5.3.2 Secondary Endpoint

Characteristic of the LFP signals correlating to presence of side effects.

5.4 Study Population

In this study we will explore the predictive capacity of LFPs recorded from STN. In total, 8 patients undergoing bilateral STN DBS and part of the PROGRESS study will be enrolled for this investigation over a 1-year period. The current surgical case load at BCM supports this level of enrollment. The details of implantation procedures and blinded trial design are given in the following sections.

5.4.1 Inclusion Criteria

To participate in this clinical investigation, the subject must meet all of the following inclusion criteria:

- Patient currently enrolled in the PROGRESS study
- Age 18-70 years
- Ability to provide informed consent
- Diagnosis of idiopathic Parkinson's disease, and DBS consensus team review supporting the placement of STN DBS.

5.4.2 Exclusion Criteria

Subjects who meet any of the following exclusion criteria must be excluded from the clinical investigation:

- Subject is not a surgical candidate;
- In the Investigator's opinion the subject unable to tolerate multiple programming sessions within a single setting;

- Subject unable to comply with the follow-up schedule

6 Procedures

Approval from the Sponsor must be received prior to initiating study procedures.

Enrolled subjects (as defined in section 6.2) will undergo DBS implant with the Infinity device according to standard clinical practice. During implantation procedure LFP will be recorded from the DBS leads contacts together with additional biometric measurements. The efficacy of stimulation will be validated intraoperatively with concurrent testing of parkinsonian features and the absence of stimulation side-effects, per clinical routine.

We will quantify the relief of symptoms through steered stimulation by contrasting the UPDRS scores before and after DBS in the outpatient clinical settings according to procedures described in the PROGRESS study for both directional and omnidirectional stimulation, and for identification of the therapeutic window. All subjects will undergo rigorous rating-scale-based assessment of the severity of their neurologic symptoms “off” and “on” PD medications, using the practically defined off state (CAPSIT-PD). Programming will be performed by an experienced clinical practitioner who is blinded to the LFP recordings and their analysis.

Following completion of this study, patients care will continue according to the PROGRESS study.

The following sections provide a detailed description of procedures required by this CIP.

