Fig.1. The schematic diagram of our blinded study design is given in the top image. The LFP and SUA recording will be obtained in the OR and information obtained from both modalities will be used for track selection. Intraoperative LFP recordings will be obtained simultaneously with SUA from three trajectories identified by stereotactic imaging (A). The microelectrodes will be inserted towards the estimated target with a Neurodrive (B) to localize characteristic SUA or excessive LFP activity in the STN (D). After the identification of optimal track and depth, a directional DBS electrode (E) with 1-3-3-1 configuration will be implanted temporarily. LFP recordings will be obtained from all 8 contacts of the directional lead and will be processed in real-time intraoperatively with a system developed in [name] laboratory. The neurologist will be blinded to these LFP recordings (F). The therapeutic window will be studied with the implanted electrode by generation of the stimulation with 6 unidirectional and one omnidirectional pattern (G and E). The outcome of the unidirectional stimulation will be

4 Device(s) Under Investigation

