Then the directional lead will be implanted and LFP signals will be recorded from all 8 contacts of the macroelectrode with 1-3-3-1 configuration. The LFP signal will be recorded from the target for 1min in resting and hand movement states (Aim-1). During these recordings, the neurologist who will test patient programming will be blinded to LFP data. Therefore, in each patient the optimal stimulation contacts will be selected without any influence from the LFP analysis.

The LFP recordings will be obtained using the gHamp biosignal amplifier (Gtec, Inc. Austria) at 2.4 kHz and 24 bit resolution. The depth information will be obtained from the Neurodrive (Alpha Omega, Nazareth, Israel), through a custom Ethernet based interface which was previously developed in [name] lab. Besides neural activity, we will record other biomedical and physiological signals with a variety of sensors, including a 2-channel bipolar electrocardiogram, 4 channel electromyogram (EMG; 2 upper and 2 lower limbs), and two 3-axis accelerometers attached to contra-lateral limbs. These signals will be entered into the multipurpose neural data acquisition system in order to synchronize behavior with the neural data. Resting and movement periods of the recording will be identified from the EMG and wireless 3-axis accelerometer sensors. The recorded data will be converted to Matlab (Mathworks, Natick MA) format, as described previously (Ince et al, 2010) for further analysis. The LFP data will be processed offline, using state-of-the-art signal processing and spectrum estimation techniques, to identify novel neuro-markers that will be used for the prediction of prediction of optimal stimulation contacts and correlation with the symptoms of the patient.

The efficacy of stimulation will be validated intraoperatively with concurrent testing of parkinsonian features and the absence of stimulation side-effects, per clinical routine. For instance, the presence of low-threshold side effects of stimulation, indicating electrode position too close to an adjacent structure—e.g., internal capsule or medial lemniscus or nucleus of cranial nerve III, when STN is the desired target—would require repositioning in order for the electrode to be clinically useful.

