7.1.1.1 Analysis Methodology

To identify the location of the DBS electrode and its contacts as well as the directionality of the segmented contacts, the intra-operative and postoperative CT and 1.5T MRI scans will be merged in stereotactic space to the preoperative imaging dataset, using the Cranial Cloud interface.

Artifact-free LFP segments at each depth will be identified by visual inspection of sensor data and video recording, and, will be subjected to spectral analysis. Power spectra of the monopolar and bipolar LFP signals will be computed using a multi-taper method, due to its low variance (Thomson 1982). Following computation of the power spectra in each 30s time segment, the power in the θ - (3-7 Hz), α - (7-13 Hz), β - (13-32 Hz), γ - (48-100 Hz) and upper gamma (200-400Hz) bands will be computed. This will provide a feature matrix representing the sub-band power levels at different depths during resting state and changes during movement-related segments for each monopolar and bipolar contact.

We will explore the dynamic LFP spectrum arising from each depth individually and investigate whether the depths related to increased β - (13-32 Hz) band power and **other frequencies** can be a predictor for the borders of the STN and optimal contacts used for DBS.

We expect that abnormal brain activity will be characterized by a preferred correlation process, reflective of the structure of the local neural elements. Abnormalities in local neural elements or circuits may produce time series with distinct autocorrelation patterns, which can then be captured by autoregressive (AR) model parameters. In brief, the AR model represents the current observation by a linear combination of the past samples and a white-noise input (Hayes 2006). The data in each epoch are assumed to be stationary, as they originate from the same depth. Each epoch is analyzed with an AR model of order p . The model is,

$$x_t = a_1 x_{t-1} + \dots + a_p x_{t-p} + e_t, \quad (1)$$

where x is the output sequence, LFP data, $a_{1..p}$ are the model parameters representing the weights of past samples, and e_t is the white noise.

This method provides a great advantage over other techniques in describing the entire length of the data in each segment by a few "subject specific" model parameters, consequently resulting in a significant

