reduction in the dimensionality of the data analysis. At each contact, the model parameters will be estimated by using Burg's Algorithm. The optimal model order will be selected based on the evaluation of three different criteria—i.e., Akaike Information Criterion (AIC), final prediction error (FPE), and minimum description length (MDL), as described previously (Hayes 2006).

Once the AR model parameters have been estimated from the LFP data, these model parameters will be used along with subband powers as characteristic features for the prediction of STN location and stimulation settings. In addition, we will investigate whether the model parameters of different DBS contacts identified during rest and movement correlate with stimulation settings. We will explore different regression and classification techniques such as linear regression, linear discriminant analysis (LDA) and support vector machine (SVM) to estimate the predictive capability of the features extracted from LFP data. The estimation of the generalization capability of the developed models will be assessed by implementing a cross validation procedure with independent learning and testing sets. This will help to clarify the extent to which the stimulation correlates with actual LFP model parameters.

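### Only the programmer is masked: the plan does not mask LFP segment marking to the clinical contact, fix a primary prediction rule, or specify cross-validation nested by patient, so concordance is at risk of upward bias

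*Combined protocol and SAP*

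**What the plan says.** The primary endpoint (5.3.1) is "Concordance between LFP derived predictions and clinically optimized stimulation parameters". The study calls itself blinded in Section 3, in 5.2.1 and in 5.3.1, where it says "we aim to determine in a blinded manner whether LFPs can guide programming". Section 5.4 announces that details of the blinded design will follow.

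The details that follow mask the clinical side:
- Section 6: "Programming will be performed by an experienced clinical practitioner who is blinded to the LFP recordings and their analysis".
- Section 6.3.1, during the recordings from the implanted lead: "the neurologist who will test patient programming will be blinded to LFP data". The legend of Fig. 1 says the same of the neurologist.
- Section 5.2.2 adds a blinded rater for the therapeutic window, who is again on the clinical side.

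On the LFP side:
- Section 7.1.1.1: "Artifact-free LFP segments at each depth will be identified by visual inspection of sensor data and video recording".
- The same section computes power in five named bands, for monopolar and bipolar signals, at rest and in movement, and leaves room for further frequencies. Autoregressive (AR) parameters are added as features, with the order judged by AIC, FPE and MDL.
- Linear regression, LDA and SVM are given as examples of methods to be explored, and none is named as primary. Cross-validation with separate learning and testing sets is planned. The unit of the split, and the steps that fall inside it, are not given.
- Sections 5.1 and 6.3.1 describe offline processing to find new markers for predicting the optimal contact. The Fig. 1 legend adds that the eight-contact recordings "will be processed in real-time intraoperatively".
- Under Section 10 the sponsor both handles and analyses the data, and under 10.2 its staff enter the CRF data. No limit on analysts' access to programming data is stated.

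**The concern.** Concordance compares two readings. Masking the programmer stops the LFP from steering the clinical choice. It does nothing about the reverse path, in which knowledge of the clinical contact steers the LFP prediction. The plan leaves three openings for that:
1. Segments could be kept or rejected by someone who knows the contact.
2. A feature, band, montage or model could be preferred because it agreed best.
3. Cross-validation could be run after that selection, or with the two leads of one patient on opposite sides of the split.

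There are at most 16 leads, so a few extra matches change the message. Sections 5.3.1 and 7.2 expect the results to provide the scientific basis for using LFPs in clinical decisions, and 7.1.1.2 intends to size a later study from these observations. An inflated concordance would carry into both.

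**Working it through.** **1. What the plan fixes and what it leaves open**

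| Safeguard | In the plan |
|---|---|
| Programmer masked to LFP | Yes (Section 6, 6.3.1, Fig. 1 legend) |
| Segment marking masked to the clinical contact | Not stated |
| One primary feature, montage and model | None named (7.1.1.1) |
| Prediction recorded before the contact is released | Not stated |
| Selection nested within cross-validation, split by patient | Not stated; only that learning and testing sets are independent |

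**2. Inputs for an illustration.** There is no figure in the plan to reproduce: 7.1.1.2 declines a power calculation, and no concordance statistic, threshold or chance level is defined.
- Leads: 8 patients × 2 (bilateral, 5.4) = 16.
- Chance match p = 1/8. This assumes that one of the eight contacts is picked and all are equally likely. Range shown: 1/6 and 1/4.
- Number of variants K: 5 bands × 2 montages × 2 states = 20; with 3 model families, 60. A smaller K = 5 is also shown.
- Type I error 0.05 (7.3), taken as one-sided because the sidedness is not given.
- No true association between LFP and clinical contact.

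**3. One rule fixed in advance (K = 1).** Matches X follow Binomial(16, 1/8). The mean is 16 × 1/8 = 2, or 12.5%. The smallest cut-off with tail probability at or below 0.05 is 5 matches, with P(X ≥ 5) = 0.0407.

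**4. Best of K variants reported.** With F the binomial distribution function and independent variants:
- expected apparent concordance = (1/16) × Σ over x = 0 to 15 of [1 − F(x)^K];
- chance that at least one variant reaches 5/16 = 1 − (1 − 0.0407)^K. For K = 20 this is 1 − 0.9593^20 = 0.564.

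The correlated column comes from 2,000 simulated pure-noise studies per setting (8 patients, 2 leads, 8 contacts), with correlation 0.8 between the variants' contact scores.

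| K | Independent: concordance; P(≥5/16) | Correlated 0.8: concordance; P(≥5/16) |
|---|---|---|
| 1 | 12.5%; 4.1% | not applicable |
| 5 | 22.5%; 18.7% | 19.2%; 13% |
| 20 | 29.6%; 56.4% | 23.7%; 27% |
| 60 | 34.4%; 91.7% | 26.6%; 40% |

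For K = 20 independent variants, chance 1/6 gives 35.5% against 16.7%, and chance 1/4 gives 46.2% against 25%.

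**5. Selection nested by patient.** In the same simulations, the variant was chosen on seven patients and applied to both leads of the eighth. Mean concordance was 12.2% to 12.7% across K = 5, 20, 60 and correlations 0, 0.5, 0.8. A plain binomial test at 5/16 still rejected in about 7% to 14% of runs, so those matches need a permutation test.

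**6. What this does not measure.** The figures describe choosing the best-scoring variant. They do not estimate the effect of unmasked segment marking, and the plan gives nothing from which to size it. Nesting would not remove that effect, because segments are chosen before cross-validation starts.

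**The case against.** A reader might infer that analysts choose features and models by eye with the clinical contact in front of them, and that the concordance is therefore biased. The documents do not support that:
- Only artifact-free segments are chosen visually, and from sensor data and video. Five bands are named, both montages are computed, and AR order rests on formal criteria.
- The reference to each depth and to 30-second segments matches the microelectrode recordings in 6.3.1, whereas the eight-contact recordings last one minute per state. It is unclear how far visual marking touches the contact data. Rejecting segments for movement artifact is also a weak way to favour one contact over another.
- The offline analysis is not placed before or after programming. The Fig. 1 legend has LFPs processed in the operating room, and 1.9 compares the clinical settings with predictions from data collected at implant. Sponsor handling of both data sets makes access possible but does not establish it.
- Cross-validation is planned, and nested selection would remove the bias shown above. Section 7.3 also promises adjustment of the family-wise error. Nothing says that only the best variant will be reported.
- This is an eight-patient pilot, and supervised learning needs the clinical contacts as labels.

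All of this stands, and it limits the point to a risk. It does not close the gap. Real-time processing is described, but nothing makes its output the scored prediction, and 6.3.1 ties prediction to the offline markers. The cross-validation text does not say what is nested or how patients are split. Section 7.3 names neither the family of tests nor the method. Section 7 allows a separate SAP for further detail, but its list of contents does not mention masking.

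**Conclusion.** The point holds as a gap in specification that puts the primary concordance at risk of upward bias. It does not hold as a demonstrated bias: the plan neither says that the clinical contact is seen first nor that the most favourable variant will be reported.

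Under no true association, 16 leads and chance 1/8, selecting among 20 variants would show about 24% (correlation 0.8) to 30% (independent) concordance where 12.5% is the truth. Nesting the selection by patient brings it back to about 12.5%. These sizes depend on the assumed chance level, number of variants and correlation, and they concern variant selection only. The change is worth making because it is cheap and protects the one primary endpoint.

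**What to change.** Amend 7.1.1.1 and Section 6 as follows.

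1. **Masked, locked features.** Segment marking and feature computation are completed and locked by staff without access to programming, therapeutic-window or side-effect data.
2. **One untrained primary rule.** Fix it in advance, for example the contact with the highest power in one pre-named band and montage, and define what counts as a match. Time-stamp the predicted contact for each lead before that lead's clinical contact is released. Report this as the primary result.
3. **Trained models, reported separately.** Nest all feature, AR-order and model selection inside leave-one-patient-out cross-validation, with both leads of a patient held out together. Test with a permutation test at patient level that repeats the whole selection. Clinical contacts may be released for this step once all features are locked, so the lock does not conflict with training on other patients. Label any further exploration as such.

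The cost is protocol and SAP wording and a data-release log. Depending on current roles, segment marking may have to move to someone without access to the clinical data. Aim 2 can still link LFPs to side effects after the lock. The downside is that the reported concordance may be less favourable than a best result picked afterwards.

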6.1 Informed Consent Process

The Principal Investigator or his/her authorized designee will conduct the Informed Consent Process, as required by applicable regulations and the center’s IRB/EC. This process will include a verbal discussion with the subject on all aspects of the clinical investigation that are relevant to the subject’s decision to participate, such as details of clinical investigation procedures, anticipated benefits, and potential risks of clinical investigation participation. During the discussion, the Principal Investigator or his/her authorized designee will avoid any improper influence on the subject and will respect subject’s legal rights. The subject shall be provided with the informed consent form written in a language that is understandable to the subject and has been approved by the center’s IRB/EC. The subject shall have adequate time to review, ask questions and consider participation.

If the subject agrees to participate, the Informed Consent form must be signed and dated by the subject and by the person obtaining the consent. The signed original will be filed in the subject’s hospital or research charts, and a copy will be provided to the subject.

The Principal Investigator or his/her authorized designee will document the informed consent process in the subject’s hospital and/or research charts. The date of signature will be entered on an applicable Case Report Form (CRF).

Failure to obtain informed consent from a subject prior to clinical investigation enrollment should be reported to Sponsor within 5 working days and to the reviewing center’s IRB/EC according to the IRB’s/EC’s reporting requirements.

If, during the clinical investigation, new information becomes available that can significantly affect a subject’s future health and medical care, the Principal Investigator or his/her authorized designee will provide this information to the subject. If relevant, the subject will be asked to confirm their continuing informed consent in writing.

6.2 Point of Enrollment

Subject is considered enrolled in the clinical investigation from the moment the subject has provided a written Informed Consent and has been confirmed to meet all inclusion criteria and none of the exclusion criteria.

The Principal Investigator or delegated study personnel will record enrollment information (name of the clinical investigation, date of consent and Inclusion/exclusion information) in the hospital records and complete and submit an applicable CRF in a timely manner.

Notification of enrollment to the Sponsor is considered to have occurred when the Sponsor has received the applicable CRF.

6.3 Scheduled Procedures

The Principal Investigator is responsible for ensuring all clinical investigation data is collected as required per CIP scheduled procedures.

